## **Visit 1**

Subjects who are interested in participating will sign the consent form. A screening physical exam will be done, and vital signs (blood pressure, heart rate, pulse rate, respiratory rate) will be measured. Pregnancy test will be done for women of childbearing potential.

Subjects will go home with sleep logs, which are subject records of when they go to sleep and wake up. They will also be given an actiwatch to wear, as an objective measure of sleep and wake periods.

The headache diaries are given which are subject records of the frequency and intensity of their migraines. They will complete the logs for one month.

## **Visit 2**

Subjects will be scheduled for a follow up at FH one month after the first Visit.

Subjective sleep symptoms will be evaluated using validated instruments, including Pittsburgh Sleep Quality Inventory (PSQI), and severity of insomnia - Insomnia Severity Index (ISI), and daytime sleepiness Epworth Sleepiness Scale (ESS), and daily visual analog scale (Karolinska sleepiness scale, KSS).

Objective sleep assessment will be performed using ambulatory 72 hour EEG, using sleep montage per standard AASM criteria, and scored by a registered polysomnography technologist using AASM guidelines. If the subject expresses hesitation because of the 72 hour EEG, then a 48 hour EEG will be offered.

Assessment of sympathetic autonomic nervous system function will be done by measuring cortisol and catecholamine levels using standard assays.

Subjects will continue to wear the actiwatch and complete sleep/Headache logs daily.

### **Visit 3**

Subjects will return for the EEG to be removed. Subjects will be given a Bioboosti for the treatment phase and instructed on how to use it. He/she will in turn instruct the participants with this information. Subjects will continue to use the actiwatch.

### **Treatment phase**

There will be one month of treatment with Bioboosti. Subjects will be asked to use the device once a day, at approximately one hour prior to initiation of habitual sleep time. They will complete up to 6 therapy cycles. A therapy cycle consists of placing the Bioboosti on the Laogong point, which is located at the center of the palm. The device will remain there for 8 minutes, and this counts as 1 cycle. When the light on the device changes, it indicates that 8 minutes have passed, and a cycle is completed. The subject will then remove the device and replace it on the Laogong point of the other hand. The subject will repeat this up to 6 times, alternating the treatment cycles between one hand to another.

They will complete sleep/headache logs for one month, as well as wear the actiwatch.

During this time, subjects should not drive while using the Bioboosti. They will also be advised to maintain a healthy lifestyle, as is done during clinic visits (light diet, regular exercise, smoking cessation, abstinence and sufficient sleep), but these are not terms of exclusion from the study.

They will be instructed to use their usual migraine abortive treatments that were utilized during the run-in phase of data collection, and to avoid the introduction of any new therapies during the treatment phase.

### **Visit 4**

Subjects will return after the one month of treatment. They will return the completed sleep logs.

Subjective sleep symptoms will be evaluated using validated instruments including, Pittsburgh Sleep Quality Inventory (PSQI), and severity of insomnia - Insomnia Severity Index (ISI), and daytime sleepiness Epworth

Sleepiness Scale (ESS), and daily visual analog scale (Karolinska sleepiness scale, KSS).

Objective sleep assessment will be performed using ambulatory 72 hour EEG, using sleep montage per standard AASM criteria, and scored by a registered polysomnography technologist using AASM guidelines. If the subject expresses hesitation because of the 72 hour EEG, then a 48 hour EEG will be offered.

Assessment of urine cortisol and catecholamines will be done as a measure of sympathetic function.

Subjects will continue to wear the actiwatch and complete sleep/headache logs daily.

### **Visit 5**

Subjects will return for the EEG to be removed. They will return the Bioboosti.

They will be asked to continue keeping the sleep/headache logs for another month.

The Bioboosti devices will be checked on their return to the study staff. If it is determined that the device is not functioning properly, the participant will be asked to redo the study.

### **Visit 6**

Subjects will return the completed sleep/headache logs. They will return the actiwatch.

For studies involving treatment or diagnosis, provide information about standard of care at Partners (e.g., BWH, MGH) and indicate how the study procedures differ from standard care. Provide information on available alternative treatments, procedures, or methods of diagnosis.
--------------------------------------------------------------------------------------------------------------------------------------------------------------------------------------------------------------------------------------------------------------------------------------

This study does not involve diagnosis. Other than the Bioboosti, the Principal Investigator will not make changes to the patient's medication regimen. Other treatments that are available to treat insomnia include: healthy sleep hygiene, antihistamines and some prescription medicines like Ambien and Lunesta.

As an alternative to standard care, we are proposing to test the Bioboosti device as a possible safe, non-pharmacologic treatment option for insomnia.

Describe how risks to subjects are minimized, for example, by using procedures which are consistent with sound research design and which do not unnecessarily expose subjects to risk or by using procedures already being performed on the subject for diagnostic or treatment purposes.

Risks of participation may include fatigue from completing the questionnaires and feelings of unease answering questions. We will make every attempt to schedule and perform the tasks so as to reduce these risks. Subjects may refuse to answer any question that upsets them.

When wearing the ambulatory EEG, subjects may feel soreness or see reddening of the skin from the glue that is used. There is a risk that the cables could become wrapped around the neck, so they should tape the cables to their back when sleeping. A registered polysomnography technologist will administer the ambulatory EEG so as to minimize these risks.

Subjects may feel discomfort when wearing the actiwatch. The strap is adjustable for their comfort.

Collection of specimen data will be done as in routine care.

Based on previously acquired data from the company, we do not anticipate any significant likelihood of adverse events. The device has been cleared for safety by the FDA. While we don't anticipate any serious adverse events, it is possible that the patients enrolled in the study experience adverse effects of the Bioboosti. To minimize risks to subjects, proper use of the bioboosti will be explained to them once the device is provided. They will be asked to use only the charger that accompanies the Bioboosti; they cannot use it while it is charging, as it will not be able to provide therapy while charging. They will not use the device when engaging in extreme sports, showering or immersing in water. As a possible device for treating insomnia, subjects may experience sleepiness when using it. As a precaution, they should not to drive while using the Bioboosti. Subjects should handle the device with care from trauma so as not to damage it, as well as keeping the device from places that are damp, extremely cold or hot, exposure to direct sunlight, near any strong magnetic field or microwave field.

Risks will be explained and subjects encouraged to ask questions. In addition to the treating physician, we will monitor for any adverse events that might be related to the device. Side effects subjects might experience due to the Bioboosti will be immediately reported to the treating physician, PI, IRB for major adverse effects as well as sponsor. If any significant events occur, these may lead to the need to discontinue the treatment.

Describe explicitly the methods for ensuring the safety of subjects. Provide objective criteria for removing a subject from the study, for example, objective criteria for worsening disease/lack of

improvement and/or unacceptable adverse events. The inclusion of objective drop criteria is especially important in studies designed with placebo control groups.

Based on previously acquired data from the company, we do not anticipate any significant likelihood of adverse events. The device has been cleared for safety by the FDA. While we do not anticipate any serious adverse events, it is possible that the patients enrolled in the study experience adverse effects of the Bioboosti.

To minimize risks to subjects, proper use of the Bioboosti will be explained to them once the device is provided, as described above. A manual on how to use the device will accompany it. A follow-up phone call will be conducted 1-2 days after the participant receives the Bioboosti to go over proper use if needed. A registered polysomnography technologist will administer the ambulatory EEG. Collection of specimen data will be done as in routine care. Risks will be explained and subjects encouraged to ask questions.

In addition to the treating physician, we will monitor for any adverse events that might be related to the device. Side effects subjects might experience due to the Bioboosti will be immediately reported to the treating physician, PI, IRB for major adverse effects as well as sponsor. If any significant events occur, these may lead to the need to discontinue the treatment

#### **FORESEEABLE RISKS AND DISCOMFORTS**

Provide a brief description of any foreseeable risks and discomforts to subjects. Include those related to drugs/devices/procedures being studied and/or administered/performed solely for research purposes. In addition, include psychosocial risks, and risks related to privacy and confidentiality. When applicable, describe risks to a developing fetus or nursing infant.

We do not anticipate any serious risks to subjects. Subjects may experience discomfort due to fatigue from completing the questionnaires and feelings of unease answering questions. We will make every attempt to schedule and perform the tasks so as to reduce these risks. Subjects may refuse to answer any question that upsets them.

When wearing the ambulatory EEG, subjects may feel soreness or see reddening of the skin from the glue that is used. There is a risk that the cables could become wrapped around the neck, so the cables should be taped to the back especially when sleeping.

Subjects may feel discomfort when wearing the actiwatch. The strap is adjustable for their comfort.

As subjects will be starting a new treatment as part of their clinical care while in the study, they may experience side effects to the Bioboosti. Based on previously acquired data from the company, we do not anticipate any

significant likelihood of adverse events. The device has been cleared for safety by the FDA. As a possible device for treating insomnia, subjects may experience sleepiness when using it. As a precaution, they should not to drive while using the Bioboosti.

Subjects will be instructed to report any side effects and/or adverse events they experience. Side effects will be immediately reported to the treating physician and PI, and will be addressed accordingly. However, if any significant events occur, these may lead to need to discontinue the treatment. Per regulatory guidelines, adverse events will be reported to the company.

### **EXPECTED BENEFITS**

Describe both the expected benefits to individual subjects participating in the research and the importance of the knowledge that may reasonably be expected to result from the study. Provide a brief, realistic summary of potential benefits to subjects, for example, "It is hoped that the treatment will result in a partial reduction in tumor size in at least 25% of the enrolled subjects." Indicate how the results of the study will benefit future patients with the disease/condition being studied and/or society, e.g., through increased knowledge of human physiology or behavior, improved safety, or technological advances.

There is no direct benefit to subjects. The Bioboosti is an FDA-approved device for the treatment of insomnia. If successful, though there is not sufficient data, subjects may experience longer, more consolidated sleep after treatment with Bioboosti and this improved sleep will lead to lesser subjective daytime sleepiness. The device may help patients with migraine by lowering the frequency/intensity of headaches, in addition to improving their sleep.

### **EQUITABLE SELECTION OF SUBJECTS**

The risks and benefits of the research must be fairly distributed among the populations that stand to benefit from it. No group of persons, for example, men, women, pregnant women, children, and minorities, should be categorically excluded from the research without a good scientific or ethical reason to do so. Please provide the basis for concluding that the study population is representative of the population that stands to potentially benefit from this research.

The subjects for this study will be recruited from the sleep clinics at BWH and FH, and will be representative of the population. As we are unsure of the effects that the Bioboosti has on the general population, and in turn the various effects of chronic conditions on a person's sleep, we will exclude patients with known untreated moderate or severe sleep apnea, or with major circadian rhythm disorders, as these may confound our analyses. We will also exclude patients who are pregnant or breastfeeding; patients with cardiac pacemaker; any electrical devices; patients with cancer; patients

with severe conditions related to heart, brain, kidney and hematopoietic system; patients with severe/unstable angina pectoris, arteria coronaria/peripheral arterial bypass graft, congestive heart failure, renal insufficiency, mechanical intestinal obstruction.

When people who do not speak English are excluded from participation in the research, provide the scientific rationale for doing so. Individuals who do not speak English should not be denied participation in research simply because it is inconvenient to translate the consent form in different languages and to have an interpreter present.

Questionnaires are validated in English. We will not be strictly excluding nonEnglish speakers, however given the small number of subjects and the large number of information that will be communicated verbally and standardized questionnaires, we anticipate that this would be easier for English speakers to participate in the study.

Patients who do not speak English will not be excluded from this study. We will provide potential non-english speaking subjects with the IRB approved short form consent form in their native language. Given that we do not anticipate enrolling more than a significant number of non-English speaking subjects, we will not have the IRB-approved long-form consent translated. A hospital medical interpreter will be scheduled to be present during the consent process and entire screening visit.

For guidance, refer to the following Partners policy:

Obtaining and Documenting Informed Consent of Subjects who do not Speak English  
[https://partnershealthcare-public.sharepoint.com/ClinicalResearch/NonEnglish Speaking Subjects.1.10.pdf](https://partnershealthcare-public.sharepoint.com/ClinicalResearch/NonEnglish%20Speaking%20Subjects.1.10.pdf)

## RECRUITMENT PROCEDURES

Explain in detail the specific methodology that will be used to recruit subjects. Specifically address how, when, where and by whom subjects will be identified and approached about participation. Include any specific recruitment methods used to enhance recruitment of women and minorities.

The BWH and FH sleep/hedache clinics will be screened for patients who are diagnosed with insomnia and patients with both insomnia and migraine. Study staff will notify the treating physician to inform them of a potential subject. The treating physician will first introduce the study to the potential subject. If the subject gives permission and would like to obtain more information regarding the study, study staff will approach them and provide them with a copy of the consent form to review. Study staff may also contact the subject by phone to explain the study and recruit if it is more convenient for the subject. Study staff and a physician investigator will be

available to answer all questions. The physician investigator will be available to speak with subjects during the consent process.

Provide details of remuneration, when applicable. Even when subjects may derive medical benefit from participation, it is often the case that extra hospital visits, meals at the hospital, parking fees or other inconveniences will result in additional out-of-pocket expenses related to study participation. Investigators may wish to consider providing reimbursement for such expenses when funding is available

Subjects will be paid \$400.00 if they complete the study. They will receive \$100 after the first EEG and the remaining \$300 at the end of the study. If subjects do not complete the study, they will not be paid for their participation. Damage to the devices or unreturned devices is equivalent to incompleteness of the study. We will also cover the cost of parking up to \$40.00 for the subject's study visits.

**Sustained Efficacy Phase:** Subjects will be paid \$350.00 for their participation. They will receive \$50.00 after the first 3 follow-up and the remaining \$200.00 at the end of the study and cover the cost of the parking for up to \$5.00 each visit. Damage to the devices or unreturned devices is equivalent to incompleteness of the study.

For guidance, refer to the following Partners policies: Recruitment of Research Subjects [https://partnershealthcare-public.sharepoint.com/ClinicalResearch/Recruitment Of Research Subjects.pdf](https://partnershealthcare-public.sharepoint.com/ClinicalResearch/Recruitment%20Of%20Research%20Subjects.pdf)

Guidelines for Advertisements for Recruiting Subjects [https://partnershealthcare-public.sharepoint.com/ClinicalResearch/Guidelines For Advertisements.1.11.pdf](https://partnershealthcare-public.sharepoint.com/ClinicalResearch/Guidelines%20For%20Advertisements.1.11.pdf)

Remuneration for Research Subjects [https://partnershealthcarepublic.sharepoint.com/ClinicalResearch/Remuneration for Research Subjects.pdf](https://partnershealthcarepublic.sharepoint.com/ClinicalResearch/Remuneration%20for%20Research%20Subjects.pdf)

## CONSENT PROCEDURES

Explain in detail how, when, where, and by whom consent is obtained, and the timing of consent (i.e., how long subjects will be given to consider participation). For most studies involving more than minimal risk and all studies involving investigational drugs/devices, a licensed physician investigator must obtain informed consent. When subjects are to be enrolled from among the investigators' own patients, describe how the potential for coercion will be avoided.

The BWH and FH sleep clinics will be screened for patients who have been diagnosed with insomnia and patients with both insomnia and migraine. Study staff will notify the treating physician to inform them of a potential

subject. The treating physician will first introduce the study to the potential subject. If the subject gives permission and would like to obtain more information regarding the study, study staff will approach them and provide them with a copy of the consent form to review. Study staff may also contact the subject by phone to explain the study and recruit if it is more convenient for the subject. Study staff and a physician investigator will be available to answer all questions. If the potential subject is interested in participating in the study, the Principal Investigator will consult with the treating physician prior to enrolling the subject. The subject will be encouraged to ask questions. If the subject is still unsure if he/she wants to participate, he/she will be encouraged to take the consent form home to consider it further. In that case a second visit will be scheduled, the consent form reviewed again, and, if signed, study procedures performed. If the subject decides to sign informed consent at the time the study is introduced, we will proceed with Visit One (Enrollment Visit) that same day. The physician investigator will be available to speak with subjects during the consent process.

NOTE: When subjects are unable to give consent due to age (minors) or impaired decisionmaking capacity, complete the forms for Research Involving Children as Subjects of Research and/or Research Involving Individuals with Impaired Decision-making Capacity, available on the New Submissions page on the PHRC website:

<https://partnershealthcare.sharepoint.com/sites/phrmApply/aieipa/irb>

For guidance, refer to the following Partners policy:  
Informed Consent of Research Subjects:

[https://partnershealthcare-public.sharepoint.com/ClinicalResearch/Informed\\_Consent\\_of\\_Research\\_Subjects.pdf](https://partnershealthcare-public.sharepoint.com/ClinicalResearch/Informed_Consent_of_Research_Subjects.pdf)

## **DATA AND SAFETY MONITORING**

Describe the plan for monitoring the data to ensure the safety of subjects. The plan should include a brief description of (1) the safety and/or efficacy data that will be reviewed; (2) the planned frequency of review; and (3) who will be responsible for this review and for determining whether the research should be altered or stopped. Include a brief description of any stopping rules for the study, when appropriate. Depending upon the risk, size and complexity of the study, the investigator, an expert group, an independent Data and Safety Monitoring Board (DSMB) or others might be assigned primary responsibility for this monitoring activity.

NOTE: Regardless of data and safety monitoring plans by the sponsor or others, the principal investigator is ultimately responsible for protecting the rights, safety, and welfare of subjects under his/her care.

The Principal Investigator, [name], will be responsible for overseeing the safety of the subjects in this study. After the first subject is

enrolled, she will meet with the study coordinator weekly to review the adverse event data collected at each study visit. She will also review any complaints about the research at this time. The Principal Investigator and study coordinator will review all data collected to ensure that all subjects complete questions and logs accurately.

If a subject decides to forgo continuation of the study, the research team will ensure their withdrawal in the safest manner possible.

Describe the plan to be followed by the Principal Investigator/study staff for review of adverse events experienced by subjects under his/her care, and when applicable, for review of sponsor safety reports and DSMB reports. Describe the plan for reporting adverse events to the sponsor and the Partners' IRB and, when applicable, for submitting sponsor safety reports and DSMB reports to the Partners' IRBs. When the investigator is also the sponsor of the IND/IDE, include the plan for reporting of adverse events to the FDA and, when applicable, to investigators at other sites.

NOTE: In addition to the adverse event reporting requirements of the sponsor, the principal investigator must follow the Partners Human Research Committee guidelines for Adverse Event Reporting

Adverse events will be reported to the Principal Investigator weekly. Any serious adverse events will be reported within 24 hours.

Adverse events that are serious, unexpected, and related or possibly related to the research study will be reported to the IRB within 5 working days/ 7 calendar days after the investigator becomes aware of the event.

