**VERSION DATE**

**06/04/2018**

**SPECIFIC AIMS**

Concisely state the objectives of the study and the hypothesis being tested.

**Hypothesis 1:** Patients with insomnia have longer, more consolidated sleep after treatment with Bioboosti.

**Specific Aim 1:** This hypothesis will be tested in a prospective study, using within subject comparisons, whereby sleep measures before treatment are compared to those after treatment.

**Hypothesis 2:** Sleep improvement will lead to a lesser subjective daytime sleepiness and reduction in migraine frequency/intensity.

**Specific Aim 2:** This hypothesis will be tested by comparing subjective measures of sleepiness, measured by standard instruments (Epworth sleepiness scale score, ESS, Karolinska sleepiness scale KSS), relative to total sleep time and wake after sleep onset. Migraine frequency and intensity will be recorded using standardized headache diaries.

**Exploratory aim:** To evaluate the physiological mechanisms, by which Bioboosti may exert its effect on sleep and overall health. This will be accomplished by a measurement of hormones directly affecting sleep and

sympathetic autonomic nervous system (urinary cortisol and catecholamines), immune, as well as autonomic function.

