### **Arm 1**

**Aim 1:** To test the hypothesis that treatment with BioBoosti has sustained efficacy in treating insomnia.

Our primary endpoint would be insomnia symptoms after 1 year of BioBoosti use as compared to initial symptoms (prior to starting treatment).

Measurement of insomnia will be done in serial comparisons every 3 months for ISI, TST (Total Sleep Time), WASO (Wake After Sleep Onset), as well as PSQI at year 1. We will use repeated measures ANOVA to compare ISI, TST, WASO, at months 3, 6, 9, and 12 and a T-test to compare PSQI at baseline to that after 1 year.

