### **Visit 5**

Subjects will return for the EEG to be removed. They will return the Bioboosti, actiwatch and completed sleep logs.

The Bioboosti devices will be checked on their return to the study staff. If it is determined that the device is not functioning properly, the participant will be asked to redo the study.

Testing of each patient requires about one month as outlined above. With efficient recruitment and minimal attrition rate, 20 participants can complete the study.

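### No outcome assessment is planned for subjects who withdraw or stop the device, so the before-after results rest by default on those who stayed and could favour the device if poor responders leave

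*Combined protocol and SAP*

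**What the plan says.** The one rule for a subject who leaves is in Data and Safety Monitoring: "If a subject decides to forgo continuation of the study, the research team will ensure their withdrawal in the safest manner possible". It concerns safety and does not mention outcome data.

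Stopping the device is treated separately. The risk and safety text after Visit 6 of the migraine schedule says "If any significant events occur, these may lead to the need to discontinue the treatment", and Foreseeable Risks and Discomforts repeats the point: "if any significant events occur, these may lead to need to discontinue the treatment". Neither place says whether such a subject continues to be assessed.

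Post-treatment measurement is tied to finishing the treatment period:

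- Insomnia group, Visit 4: PSQI, ISI, ESS, KSS and EEG after the two weeks of treatment.
- Insomnia and migraine group, Visit 4: the same set after one month of treatment.
- Sustained Efficacy Phase: ISI and PSQI at months 3, 6, 9 and 12, with ESS only at month 12.

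Specific Aims describes the comparison as "using within subject comparisons, whereby sleep measures before treatment are compared to those after treatment", so there is no control arm. For the 1-year phase, Arm 1 states "Our primary endpoint would be insomnia symptoms after 1 year of BioBoosti use as compared to initial symptoms" and names the methods: "We will use repeated measures ANOVA to compare ISI, TST, WASO, at months 3, 6, 9, and 12", plus a t-test of PSQI at baseline against 1 year. No analysis set, missing-data rule or dropout rate is given. Visit 5 of the insomnia schedule only expects attrition to be minimal.

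**The concern.** In an open, uncontrolled study of a device used every day, subjects who notice no benefit or feel worse may well be the ones who leave. If their outcomes are not collected, the before-after change describes those who stayed, and no comparison group suffers a similar loss that might offset it. Statistical modelling afterwards is a weak substitute: for someone who leaves the short phase before Visit 4 there is no post-treatment questionnaire score to model. Data collection has to be settled in the protocol, before subjects leave.

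**Working it through.** The plan gives no alpha, power, effect size, SD or dropout rate, so it has no figure of its own to reproduce. The check has two parts.

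**1. What a leaver contributes under the schedule as written**

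| Subject | Post-treatment ISI, PSQI, ESS | Other data that may survive |
|---|---|---|
| Leaves the short phase before Visit 4 | None scheduled | Actiwatch and sleep logs (and headache diaries in the migraine group) up to leaving, if returned |
| Leaves the 1-year phase | None after the last visit attended | ISI and PSQI from visits attended; actiwatch from the month before each of those visits |
| Stops the device, stays in the study | Not stated | Not stated |

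A paired t-test needs both values, and repeated measures ANOVA in its standard form needs every time point. Rows one and two therefore drop out of the questionnaire analyses by default.

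**2. How much this could matter (illustration only)**

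From the documents: n = 20 per group and a within-subject comparison. Assumed: two-sided alpha 0.05, so a nominal 2.5% chance of a false finding of benefit; true mean change 0; change Y ~ N(0,1) in SD units, positive meaning improvement.

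Leaving follows a logistic model, logit P(leave) = a − ln(OR)·Y. OR is the ratio of the odds of leaving per SD of worse change, and a is set to give withdrawal fraction f. The stayers' mean is E[Y·(1 − P(leave))]/(1 − f). False benefit is the share of 40,000 simulated trials in which a t-test on stayers is significant in favour of the device.

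| Withdrawal f | OR per SD | Shift of stayers' mean | False benefit |
|---|---|---|---|
| 25% | 1 (unrelated to response) | 0 | about 2.5% |
| 5 to 10% | 1.5 to 2 | small | about 3 to 4.5% |
| 25% | 2 to 3 | 0.16 to 0.23 SD | about 8 to 14% |

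If 75% of leavers gave a score that truly represented their endpoint, the last row would fall to about 3.5 to 4%.

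A second dropout model gives the same picture. Let the fraction d with the lowest latent score leave, where that score correlates rho with benefit. The shift is rho·φ(z(1−d))/(1 − d). With rho = 0.5:

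- d = 10%: 0.5 × 0.1755/0.9 = 0.10 SD, false benefit about 6%.
- d = 20%: 0.5 × 0.280/0.8 = 0.175 SD, about 10%.
- d = 30%: 0.5 × 0.348/0.7 = 0.25 SD, about 15%.

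With rho = 0 there is no shift. With rho = −0.3, where good responders leave, the shift reverses to −0.06, −0.11 and −0.15 SD, and false benefit falls to about 1%.

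**The case against.** The case against has real substance.

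- **The text is silent; it does not order release.** A reader might infer that leavers are sent away unmeasured. The withdrawal sentence neither requires nor forbids an assessment, and the consent pages, which may address withdrawal, are not in the text available. This stands: the defect is an omission.
- **Stopping the device is not said to end measurement.** A reader might infer that it does. The documents use different words for discontinuing treatment and for leaving the study, and nothing cancels later visits for a subject who is off the device. This stands: the plan is unclear on the point.
- **Not all data are lost.** Actiwatch and logs run through the short treatment phase, and the 1-year phase has three-monthly scores. This stands for sleep time and wakefulness, and for partial 1-year data. It does not supply the missing Visit 4 questionnaires.
- **No contact with leavers is guaranteed.** Visit 5 of the insomnia schedule says "They will return the Bioboosti, actiwatch and completed sleep logs", but it describes completers. The remuneration text only treats unreturned devices as non-completion. A return visit by a leaver can be hoped for but not assumed.
- **An exit score is not a 1-year value.** A score taken in month 2 has no place in an analysis of month 12. This stands and limits the remedy.
- **This is an uncontrolled pilot.** Even complete follow-up would not let the change be attributed to the device. That is true, but the before-after change is still the study's main result, and it should describe everyone given the device.

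**Conclusion.** The gap is real. The plan schedules no outcome assessment for a subject who withdraws, does not say whether one who stops the device is still assessed, and has no missing-data rule. With the named methods and no control arm, the results would by default rest on those who stayed.

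A reader might go further and conclude that the results will lean toward benefit. The documents do not support that. They give no dropout rate and no reasons for leaving, and the direction depends on poor responders being the ones who leave. Under that assumption, with 20 subjects and no true effect, the false-benefit rate rises from 2.5% to about 3 to 4.5% at 5 to 10% withdrawal, and to about 8 to 14% at 25%. If leaving is unrelated to response, there is no inflation. If attrition proves as small as the plan expects, the effect is modest. Because uncollected scores cannot be recovered later, the change is still worth making.

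**What to change.** Keep the safe-withdrawal sentence in Data and Safety Monitoring and add two statements:

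1. A subject who stops using the device remains on the planned assessments unless he or she withdraws consent for follow-up.
2. A subject who leaves the study is asked, in person or by phone, to complete ISI, PSQI and ESS, to return logs and actiwatch, and to give the reason for leaving.

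These concern measurement only and do not touch when or why treatment is stopped.

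In the analysis text:

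- **Short phase:** analyse everyone given the device, using the exit score as the post-treatment value for those who left.
- **1-year phase:** analyse all available visits with a mixed model. Report exit scores separately and do not carry them forward as month-12 values.
- **Both:** show the number of withdrawals and the reasons beside the result.

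The cost is a few sentences of protocol text and, for some leavers, an extra short contact. Some will decline, and the estimated benefit may be slightly smaller. The change does not remove a separate selection: entry to the 1-year phase is optional and needs fresh consent (Research Design and Methods; Sustained Efficacy Phase), so that endpoint would describe volunteers even if nobody withdrew.
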